
9.2.3. Clinical Events Defined

The chart below shows the specific clinical events that are defined as serious for the SAIL Study and the reporting requirements established for the clinical sites:

Adverse Event definitions:	Time Frame
Oxygen requirement of FiO ₂ ≥ 40% for 2 hours or more	Within the first 48 hours post delivery
Grade 1 or 2 IVH	Head ultrasound findings with the first 10 days of life (report based only)
Infant requiring > 30% Oxygen or mechanical support	Respiratory support assessment at day of life 28

Serious Adverse Event definitions:	Time Frame
Death	Within the first 48 hours post delivery
Administration of epinephrine or use of chest compressions	Within the first 48 hours post delivery
Pneumothorax, pulmonary interstitial emphysema (PIE) and pneumopericardium. These will be supplemented by data on: 
 a) any chest tube in-situ post DR b) need for new chest tube after arrival in NICU 	Radiographic evidence within the first 10 days of life
Grade 3 or 4 IVH	Head ultrasound findings with the first 10 days of life (report based only)

9.2.4. Unanticipated Problems

An Unanticipated Problem is defined as any incident, experience, or outcome that meets *all* of the following criteria:

- 1) Is not expected in terms of nature, severity, or frequency in relation to (a) the research risks that are described in the IRB-approved research protocol and informed consent document; Investigator's Brochure or other study documents, and (b) the characteristics of the subject population being studied; **and**
- 2) Is related or possibly related to participation in the research; **and**
- 3) Places subjects or others at a greater risk of harm (including physical, psychological, economic, or social harm) than was previously know or recognized.

9.2.5. Adverse Event Management and Reporting

If an adverse event meets any of the criteria listed above of Serious, Unexpected and at least Possibly Attributable to the study therapy or intervention, it will be reported by study team at the recruiting site to the NICHD, the Data Coordinating Center (DCC), and the local IRB (per site specific

IRB procedures) as a serious adverse event via the Medwatch Safety Reporting Form 3500A or a form that mimics it.

Adverse Event/Serious Adverse Event forms will be completed by site research staff (investigators and/or coordinators) for each reportable (as defined by protocol) adverse event that infants may experience from the time of randomization through the predefined intervention and/or events monitoring period. Events will be documented by clinical site staff using case report forms (CRF), reviewed and signed by the site investigator for accuracy and completeness then entered into the specified Data Management System (DMS) as instructed in the manual of procedures.

1. A preliminary SAE alert must be submitted within 24 hours of first knowledge of the event.
2. A more complete SAE report should be submitted (on Medwatch form 3500A or a similar form developed by the DCC) within 72 hours.
3. A final report must be submitted by the site to the DCC within one week, including when applicable, autopsy findings.
4. The final report will then be submitted to the DSMC Chair for independent adjudication of relatedness to the intervention.

The Program Scientist at NICHD and/or the DCC will determine whether expedited DSMC reviews are necessary. The DSMC can recommend further action and the DCC will be responsible for notification to the local site team and NICHD. NICHD may request the DCC notify required parties through established communication mechanisms via technical memos.

Reporting to the Food and Drug Administration will not be required for this trial as it involves no new drug or device intervention mandating an IND/IDE.

10. Synopsis

It is expected that trial completion in 12 sites will take 5 years, including 2.5 years of recruitment.

1. PURPOSE

The purpose of this document is to describe the methods to be used for data analysis for the Sustained Aeration of Infant Lungs (SAIL) randomized clinical trial. The methods described will cover the standard accrual, safety, and data quality reporting for presentation at SAIL Steering Committee meetings, as well as the interim and final analyses of safety and efficacy data specified in the study protocol. This plan will go into specific detail for each analysis including, where appropriate,

The endpoints or data items to be evaluated

The population or subset upon which the evaluation is being performed

Rules for handling exceptional data

The descriptive and statistical methods to be applied to each endpoint or data item

The format to be used for presenting the results

The frequency of analyses and other monitoring

The parties to whom each report will be provided

A summary of the types and frequencies of reports produced, the personnel responsible for each report, and distribution lists are given in Appendix A. Additional information regarding procedures to be followed by the SAIL Data Safety and Monitoring Committee (DSMC) are provided in the DSMC section of the SAIL Protocol.

2. STUDY DESCRIPTION

2.1 Study Design

This study is a 2-arm randomized, controlled, multi-center clinical trial to determine which of two strategies at birth are best to optimally aerate the lung of preterm infants. Treatment allocation is blinded, though implementation of intervention is not blinded. Specifically we will determine in 600 infants of 23-26 weeks gestational age (GA) requiring respiratory support at birth which of two lung opening strategies – either a standard PEEP/CPAP of 5-7 cm H2O in the delivery room (DR), as compared to early lung recruitment using Sustained Inflation (SI) in the DR, will result in a lower rate of the combined endpoint of death or Bronchopulmonary Dysplasia (BPD) (using a standardized oxygen reduction test) at 36 weeks PMA. We will also compare which has the lower rate of other important secondary outcomes including rates of neurodevelopmental impairment at 22-26 months of corrected age in survivors. A full description of the study design is contained in the study protocol.

2.2 Study Objectives

Hypotheses:

- 1. Early lung recruitment with SI superimposed upon standard PEEP/CPAP in the DR will reduce the need for mechanical ventilation in the first seven days of life, and reduce need for surfactant use; and
- 2. A policy of DR SI on standard PEEP/CPAP recruitment will confer better outcomes at 36 weeks post-menstrual age (PMA) than standard PEEP/CPAP.

Primary Aim:

1. To determine in 600 infants born at 23-26 weeks GA requiring respiratory support at birth, which of two lung opening strategies – either a standard PEEP/CPAP of 5-7 cm H2O in the DR, compared to early lung recruitment using SI in the DR, results in a lower rate of the combined endpoint of death or BPD (using a standardized oxygen reduction test) at 36 weeks PMA.

Secondary Aims:

To compare the rates of other important secondary outcomes such as:

- 1. Detailed outcomes of potential importance in the first 10 days of life:
 - a. Heart rate in the DR
 - b. Detailed status on departure from the DR
 - c. Use of inotropes on arrival in NICU
 - d. Chest X-ray reports showing pneumothorax or new chest drains in the first 48 hours of life;
 - e. Need for new chest drains after NICU admission
 - f. Duration of any chest drain in-situ post-DR
 - g. Oxygen profile over first 48 hours post DR using hourly FiO2 records
 - h. Oxygen profile with highest FiO2 up to 48 hours
 - i. Head US and/or MRI findings of intraventricular hemorrhage grades 3 and 4 by 48 hour and by day 10, if clinically available
 - j. CXR appearance between days 7-10, if clinically obtained
- 2. Components of the primary outcome (i.e. death by 36 weeks PMA or BPD at 36 weeks PMA
- 3. Need for intubation in DR or by 24 hours of age
- 4. Pressure-volume characteristics in the DR (at several but not all sites)
- 5. Death or need for positive pressure ventilation at 7 days
- 6. Highest FiO2 and Area under the curve FiO2 for first week of life
- 7. Survival to discharge home without BPD, retinopathy of prematurity (grades 3 & 4), or significant brain abnormalities on head ultrasound
- 8. Pneumothorax and pulmonary interstitial emphysema (PIE)
- 9. Duration of respiratory support (ventilation, CPAP, supplemental oxygen)
- 10. Retinopathy of prematurity (ROP) stage 3 or greater requiring treatment
- 11. Death before discharge
- 12. Use of postnatal steroids for treatment of BPD
- 13. Length of hospital stay
- 14. Neurodevelopmental and respiratory outcome at 22-26 months corrected GA

2.3 Study Endpoints

The primary endpoint for this study is both an efficacy and safety endpoint. Improved death / BPD rates suggest efficacy, while worse rates suggest a safety problem. As such, all comparisons are inherently two-sided. Interim and final analyses present the classic spectrum of decisions: superiority, non-inferiority, and inferiority.

2.3.1 Primary Efficacy Endpoint

To compare the rate of Death or BPD between the two intervention arms, with BPD being defined using a standardized oxygen reduction test. The primary endpoint will be recorded at 36 weeks PMA.

2.3.2 Secondary Efficacy Endpoints

The secondary efficacy endpoints (and associated secondary aim) are defined below. Endpoints considered adverse events / safety endpoints are given in Section 2.3.3. The timing of evaluation of each endpoint is given in bolded font.

Delivery Room (DR):

- 1. Heart rate in the DR (SA1a)
 Categorical variable with 3 levels: <60, 60-100, >100
- 2. Type of respiratory support (CPAP, PPV) on departure from DR (SA1b)
- 3. Fraction of Inspired Oxygen (FiO₂) on departure from DR (SA1b)
- 4. Pressure-volume characteristics in the DR (at several but not all sites) (SA4)
- 5. Need for intubation in DR (SA3)

First 48 hours of life:

- 6. Use of inotropes (SA1c)
 - Any use within first 48 hours of life
- 7. Pneumothorax (SA1d, SA8)

Source documentation needed for adjudicated yes/no variable

- 8. Need for new chest drains (SA1de)
 - Calculated as an increase in the number of chest drains recorded hourly.
- 9. Oxygen requirement of $Fi0_2 \ge 40\%$ for 2 hours or more (SA1g)
- 10. Highest FiO₂ level recorded during the first 48 hours post DR (SA1h)
- 11. Area under the hourly FiO₂ curve (SA6)
- 12. Need for intubation in DR or during first 48 hours of life (SA3)

First 7 days of life:

13. Death or need for positive pressure ventilation at 7 days (SA5)

First 10 days of life:

14. Need for new chest drains (SA1de)

Calculated as an increase in the number of chest drains recorded hourly for the first 48 hours, and then daily up to 10 days of life.

15. Duration of any chest drain (SA1f)

Calculated as the amount of time the number of chest drains is >0. Since this will be measured hourly for 48 hours and then daily, the finest level possible will be calculated for each infant and then the data will be examined to determine the scale for analysis.

- 16. Highest FiO₂ level recorded from 48 hours to 10 days of life (SA6)
- 17. Air leak (SA8)

Defined as radiographic evidence of pneumothorax, pulmonary interstitial emphysema (PIE) or pneumopericardium.

36 weeks PMA:

- 18. Death (SA2)
- 19. BPD defined using a standardized oxygen reduction test (SA2)

Discharge:

- 20. Retinopathy of prematurity (ROP) stage 3 or greater requiring treatment (SA10)
- 21. Death in hospital (SA11)
- 22. Survival to discharge home without BPD, retinopathy of prematurity (grades 3 & 4), or significant brain abnormalities on head ultrasound (SA7)
- 23. Length of hospital stay in days (SA13)
- 24. Use of postnatal steroids for treatment of BPD (SA12)
- 25. Duration of respiratory support (ventilation, CPAP, supplemental oxygen) in days (SA9)

22-26 Months corrected gestational age:

- 26. Neurodevelopmental outcomes (SA14)
- 27. Respiratory outcomes (SA14)

2.3.3 Safety

The primary safety endpoint is:

• Death or BPD at 36 weeks PMA.

The secondary safety endpoints are:

- Death within 48 hours of delivery.
- Oxygen requirement of Fi02 \geq 40% for 2 hours or more within the first 48 hours post delivery.
- Rate of pneumothorax, pulmonary interstitial emphysema (PIE), and pneumopericardium within the first 10 days of life. These will determined by radiographic evidence and supplemented by data on a) any chest tube in-situ post DR and b) need for new chest tube after arrival in NICU.
- Grade 3 or 4 IVH within the first 10 days of life. Head ultrasound findings will be used to determine incidence of IVH.

• Any other serious adverse events that have been adjudicated as potentially relating to the intervention. (See Protocol section 9.2.2)

Adverse events will be compared between intervention arms. Adverse event data, including all serious adverse events, will also be descriptively summarized.

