2.2. Specific Aims

- 1) To determine in 600 infants born at 23-26 weeks GA requiring respiratory support at birth, which of two lung opening strategies – either a standard PEEP/CPAP of 5-7 cm H₂O in the DR, compared to early lung recruitment using SI in the DR, results in a lower rate of the combined endpoint of death or BPD (using a standardized oxygen reduction test) at 36 weeks PMA.
- 2) To compare the rates of other important secondary outcomes such as:
 - a. Detailed outcomes of potential importance in the first 10 days of life:
 - i. Heart rate in the DR
 - ii. Detailed status on departure from the DR
 - iii. Use of inotropes on arrival in NICU
 - iv. Chest X-ray reports showing pneumothorax or new chest drains in the first 48 hours of life;
 - v. Need for new chest drains after NICU admission
 - vi. Duration of any chest drain in-situ post-DR
 - vii. Oxygen profile over first 24 hours post DR using hourly FiO₂ records
 - viii. Oxygen profile with highest FiO₂ up to 48 hours
 - ix. Head US and/or MRI findings of intraventricular hemorrhage by all grades but especially focusing on grades 3 and 4 by 48 hour and by day 10, if clinically available
 - x. CXR appearance between days 7-10, if clinically obtained
 - b. Components of the primary outcome (i.e. death by 36 weeks PMA or BPD at 36 weeks PMA)
 - c. Need for intubation in DR or by 24 hours of age
 - d. Pressure-volume characteristics in the DR (at several but not all sites)
 - e. Death or need for positive pressure ventilation at 7 days
 - f. Highest FiO₂ and Area under the curve FiO₂ for first week of life

- g. Survival to discharge home without BPD, retinopathy of prematurity (grades 3 & 4), or significant brain abnormalities on head ultrasound
- h. Pneumothorax and pulmonary interstitial emphysema (PIE)
- i. Duration of respiratory support (ventilation, CPAP, supplemental oxygen)
- j. Retinopathy of prematurity (ROP) stage 3 or greater requiring treatment
- k. Death before discharge
- l. Use of postnatal steroids for treatment of BPD
- m. Length of hospital stay
- n. Neurodevelopmental and respiratory outcome at 22-26 months corrected GA

3. Study Team

[figure not shown]

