Daily Respiratory Status for First Week of Life	Clinical: current respiratory status at noon each day to include if applicable, respiratory support (CPAP, noninvasive PPV, invasive PPV); specific ventilatory settings; surfactant administration Infant's respiratory rate, highest FiO ₂ from previous time point and corresponding SpO ₂	Completed for every day for the first week of life

Data Collection Topic	Specific Data Elements	Specific time interval
Daily Assessment for First Week of Life	
Clinical: birth weight and head circumference; antibiotics, antifungals, indomethacin or ibuprofen, caffeine or other methylxanthines; furosemide or other loop diuretic; thiazide diuretic; corticosteroids, inhaled corticosteroids, inhaled nitric oxide, inhaled bronchodilator; vitamin A IM, erythropoietin; red blood cell transfusion, any paralytic agent; any anticonvulsants, any milk feed or formula, any breast feeding and any parental nutrition
 
Clinical radiographic data, if available: head ultrasound or MRI, number of CXR, abdominal films
	Completed for every day for the first week of life
Maternal Data Form	Clinical: mother's age, gravid para status, exposure to antenatal steroids and type; maternal ethnicity; maternal education, any medications given to prolong pregnancy including tocolytics; placental abruption; chorioamnionitis; membranes rupture ≥ 24 hours before delivery; mode of delivery	Completed within one week of enrollment
Weekly Respiratory Status until 36 wks PMA	
Clinical: current respiratory status at noon once/week to include if applicable, respiratory support (CPAP, noninvasive PPV, invasive PPV); specific ventilatory settings
 
Infant's respiratory rate, highest FiO₂ from previous time point and corresponding SpO₂
	Collected weekly from 2 nd week of life until 36 weeks PMA
Weekly Assessment until 36 wks PMA	Same as above with the exception of weekly head circumference instead of at birth and date of successful extubation defined as extubation for greater than 48 hours	Can be completed once a week (does not need to be a specific day of the week)
Respiratory Status at 36 wks PMA	
Clinical data: exact 36 wks PMA date; respiratory status (RA, NC, CPAP, invasive/non-invasive PPV),
 
If applicable pass/fail Oxygen Reduction Test (ORT)
	Can be completed within one week of reaching 36 wks PMA

Data Collection Topic	Specific Data Elements	Specific time interval

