All of the standard reports described in the previous section will be provided to the DSMC with this analysis. Additional measures to be considered at the interim analysis include baseline clinical factors and adverse events. The study population for all of the analyses provided to the DSMC is the intent-to-treat population, including all participants and time points for which data have been entered and verified in the study database. A summary of the analyses to be included in the interim report is outlined below. Additional details of the statistical methods to be used are given in the next section regarding the final analysis.

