Completed 48 hours post delivery	n (%)

Table 4: Subject Accounting by Intervention Arm

	A	В	Total
Total Randomized	~n	~n	~n
Completed Study	n (%)	n (%)	n (%)
Still on Study	n (%)	n (%)	n (%)
Discontinued Study:	n (%)	n (%)	n (%)
Violation of protocol	n (%)	n (%)	n (%)
Withdrawal of consent	n (%)	n (%)	n (%)
Adverse event	n (%)	n (%)	n (%)
Other	n (%)	n (%)	n (%)

Flow of Subjects Through Study Phases

[figure not shown]

Figure 1. Flow of Subjects Through Study Phases

Table 5. Cumulative Serious Adverse Events by Intervention Arm

		A	-	В	To	tal	p-value
Number of Subjects	~n		~n		~n		
Within the first 48 hours post delivery Death Oxygen Requirement (Fi02 ≥ 40% for 2 hours or more)	n n	(%) (%)	n n	(%) (%)	n n	(%) (%)	0.xx 0.xx
Within first 10 days of life: Pneumothorax Pulmonary Interstitial Eemphysema Pneumopericardium	n n n	(%) (%) (%)	n n n	(%) (%) (%)	n n n	(%) (%) (%)	0.xx 0.xx 0.xx
Grade 3 or 4 IVH Within first month of life: BPD	n n	(%) (%)	n n	(%)	n n	(%)	0.xx 0.xx
Other: XXX	n	(%)	n	(%)	n	(%)	0.xx

Table 6. Assessment of SI Intervention

	Total
Number of SI maneuvers performed	
1	%
2	0/0
2 SIs performed by Clinical Site	
University of Pennsylvania	%
University of Melbourne	%
etc.	%
Post SI intervention Respiratory Mode	
CPAP	%
PPV	%

NB: Percentages only in SI arm to maintain blinding until study completion.

Table 7. Primary Endpoint: Death or BPD at 36 weeks PMA

	A	В	Total	
Number of Subjects Randomized	~n	~n	~n	
Death/BPD Rate (p=0.xx) Death BPD	n (%) n (%) n (%)	\ /	n (%) n (%) n (%)	

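### Grade 3-4 IVH is seen only on clinically obtained head scans, and the SAP does not say how infants who die or reach day 10 unscanned are counted

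*SAP*

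**What the plan says.** **How IVH is found.** SAP 2.3.3 lists grade 3 or 4 IVH within 10 days as a secondary safety endpoint and states that "Head ultrasound findings will be used to determine incidence of IVH". The corresponding aim in SAP 2.2 reads "Head US and/or MRI findings of intraventricular hemorrhage grades 3 and 4 by 48 hour and by day 10, if clinically available", and Protocol 2.2 carries the same limit: "by 48 hour and by day 10, if clinically available". The daily assessment row of the data table in Protocol section 5 collects "Clinical radiographic data, if available: head ultrasound or MRI, number of CXR, abdominal films". Protocol 9.2.3 makes grade 3 or 4 IVH a serious adverse event on this basis: "Head ultrasound findings with the first 10 days of life (report based only". Under Protocol 9.2.5, event forms are filled in for reportable events that occur. An unscanned infant therefore generates no IVH form.

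**How IVH is tabulated.** The IVH row sits in "Table 5. Cumulative Serious Adverse Events by Intervention Arm" (SAP Appendix B). That table has one number of subjects per arm at the top, then a count, percentage and p-value for each event. It has no entry for infants scanned. Death appears there only for the first 48 hours.

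**Population and missing data.** SAP section 4 says "The study population for all of the analyses provided to the DSMC is the intent-to-treat population", and the sentence continues "including all participants and time points for which data have been entered and verified in the study database". SAP 6.2 says that missing data will in general not be imputed and that the number included in each analysis will be reported. SAP 5.3 carries the interim safety reporting over to the final analysis.

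**The concern.** A brain hemorrhage can enter the numerator only if someone scanned the infant. In this population some infants may die in the delivery room or the first days before any scan, and others may reach day 10 alive and unscanned. The plan does not say whether they are non-events, missing values, or a category of their own.

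The direction of the error matters most. If unscanned infants stay in the denominator as non-events, a rise in very early deaths in one arm lowers that arm's IVH rate. SAP section 4 allows early stopping when serious adverse events possibly related to the study are clinically higher under the intervention. A harm rate that falls as early deaths rise is a poor input to that judgment.

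**Working it through.** The documents state no IVH rate, scan rate, early-death rate or power for IVH, so there is no figure to reproduce. What follows is an illustration on assumed rates.

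**Inputs**
- From the documents: 300 infants per arm (Protocol 6.1.1).
- Assumed: IVH risk in scanned infants p = 15% (range 10-20%); share unscanned by day 10, u, of 2% in control and 2%, 5%, 8% or 10% in the sustained inflation (SI) arm.
- Assumed where stated: unscanned infants have k times the IVH risk of scanned infants, with k = 2.

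**Formulas**
- Table 5 layout: recorded rate = (1 − u) × p. Its risk ratio, SI over control, equals the scanned-infant risk ratio times (1 − u_SI)/(1 − u_control).
- Unscanned infants dropped: recorded rate = p.
- Full risk = (1 − u) × p + u × k × p.
- Death unscanned or IVH = u + (1 − u) × p, taking every unscanned infant to have died. Deaths after a clear scan are left out of this illustration.

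**Step 1. No true difference in scanned infants, p = 15% in both arms**

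| Unscanned, control vs SI | Table 5 layout | Risk ratio | Scanned only, risk ratio | Death unscanned or IVH |
|---|---|---|---|---|
| 2% vs 2% | 14.7% vs 14.7% | 1.00 | 1.00 | 16.7% vs 16.7% |
| 2% vs 5% | 14.7% vs 14.25% | 0.97 | 1.00 | 16.7% vs 19.25% |
| 2% vs 8% | 14.7% vs 13.8% | 0.94 | 1.00 | 16.7% vs 21.8% |
| 2% vs 10% | 14.7% vs 13.5% | 0.92 | 1.00 | 16.7% vs 23.5% |

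The risk-ratio factors are 0.95/0.98 = 0.97, 0.92/0.98 = 0.94 and 0.90/0.98 = 0.92, and they do not depend on p. For p from 10% to 20%, the false gap is 0.3-0.6 points at 2% vs 5% and 0.8-1.6 points at 2% vs 10%.

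**Step 2. A real excess: 12% control vs 15% SI in scanned infants, risk ratio 1.25**
- 2% vs 5% unscanned: 0.1425/0.1176 = 1.21
- 2% vs 8%: 0.1380/0.1176 = 1.17
- 2% vs 10%: 0.1350/0.1176 = 1.15

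The excess is attenuated but stays above 1. At 2% vs 10%, only a scanned-infant risk ratio below 0.98/0.90 = 1.09 would be recorded as below 1.

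**Step 3. Does a scanned-only denominator repair it?** Take p = 15%, k = 2, 2% vs 8% unscanned.
- Full risk: 0.147 + 0.02 × 0.30 = 0.153 vs 0.138 + 0.08 × 0.30 = 0.162, risk ratio 1.06
- Table 5 layout: 0.138/0.147 = 0.94
- Scanned only: 1.00

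Neither denominator recovers 1.06. Scanned-only moves nearer but conditions on an event after randomization.

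**Step 4. Scale against chance.** At 15% and 300 per arm, the standard error of the difference is √(2 × 0.15 × 0.85/300) = 2.9 points, ignoring clustering of multiples. The gaps in Step 1 are 0.45, 0.9 and 1.2 points.

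**The case against.** A reader might infer from Table 5 that the SAP takes IVH over all subjects and scores unscanned infants as IVH-free. No sentence says so. Appendix B calls its tables examples whose content and format may change. The intent-to-treat sentence in SAP section 4 is limited to participants and time points with verified data, and SAP 6.2 rules out imputation in general. Together these could be read as excluding unscanned infants. This part of the objection stands: the defect is an undefined rule, and the downward bias follows only under the Table 5 layout.

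Two things limit how far it goes. An early death still has delivery-room and death records, and an absent event form looks like no event, so the missing-data rule may never be triggered. And exclusion brings its own problem, as Step 3 shows.

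It is also fair that early deaths are visible. Death within 48 hours is a safety endpoint, has its own row in Table 5, and reaches the DSMC as a serious adverse event. The primary endpoint includes death. Secondary endpoint 22 in SAP 2.3.2 (survival to discharge without BPD, severe retinopathy or significant brain abnormality) counts an infant who dies unscanned as a failure. No numerical boundary is set for IVH, and SAP 4.4 calls adverse event comparisons primarily descriptive. These points reduce the risk but do not remove it. Deaths from 48 hours to day 10 have no named row in Table 5 although the IVH window runs to day 10, and endpoint 22 is a discharge-time efficacy measure.

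Finally, IVH over all randomized infants, shown beside death, is a legitimate summary. That is why the IVH row should stay.

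**Conclusion.** The point holds as a gap in definition. Ascertainment depends on a clinical scan, no rule covers infants without one, and neither available reading gives a sound comparison between arms on its own.

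The size is modest and rests entirely on assumed rates. The risk ratio shifts by about 3-8% for 2% versus 5-10% unscanned, and by nothing when the shares are equal, although each arm's rate is still understated.

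A reader might go further and infer that the DSMC could be shown a favorable IVH result from an arm with substantially more brain injury. The documents do not support that. A scanned-infant risk ratio of 1.25 is still recorded as 1.15-1.21. Only a small excess, below about 1.09 in the most unequal case shown, or one lying mainly in unscanned infants as in Step 3, could be recorded as below 1. The 48-hour death row would also show much of the imbalance. The change is worth making because the error runs in the reassuring direction and the remedy is cheap.

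**What to change.** In SAP 2.3.3 and Table 5:

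1. Keep the grade 3-4 IVH row and state its denominator and how unscanned infants are classified.
2. Add, by arm, the number scanned by day 10 and the number who died by day 10 without a scan.
3. Add death or grade 3-4 IVH by day 10, over all randomized infants, as a supporting between-arm safety comparison. The plan already combines death with a competing outcome in the primary endpoint and in death or positive pressure ventilation at 7 days.
4. If a percentage among scanned infants is shown, label it descriptive.

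**Cost.** A sentence of SAP wording and a few table rows, with no new procedure. Imaging, IVH grade and date of death are already collected. Because daily forms end at one week and weekly forms follow, the data center should confirm that a scan on days 8 to 10 can be dated. The downside is one more safety comparison, and the composite mixes two harms, so its components should stay listed separately.
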